6.2 Efficacy Analysis

This is a safety trial. Efficacy will not be formally evaluated.

6.3 Safety Analysis

6.3.1 Adverse Events

Adverse events recorded from the time the Informed Consent Form is signed until 30 days after the end of the trial will be captured in the trial safety database. For any AE included in this trial's safety database, follow-up information on the AE up to 30 days from the onset of the AE will also be included in the same database. Post-trial AEs not included in this database will be included in a separate pharmacovigilance database, which will be used for generating periodic safety reports.

Treatment-emergent adverse events (TEAEs) will be used for summary and analysis purposes.

All TEAEs will be coded by system organ classification and preferred terms according to version 15.0 of MedDRA®.

When AE start and/or stop dates are missing, the following imputations will be made (subject to medical review):

Missing AE Start Dates

- 1. If onset date is completely missing, then onset date is set to date of first dose
- 2. If year is present and (month and day are missing), or (month is missing but day is present):
 - a. If year = year of first dose, then set date to first dose date
 - b. If year < year of first dose and medication stop month and year are available, then set to first of the end month
 - c. Otherwise if year < year of first dose, then set month and day to December 31st.
 - d. If year > year of first dose, then set month and day to January 1st.
- 3. If month and year are present and day is missing:
 - a. If year=year of first dose and
 - i. If month = month of first dose then set day to day of first dose date
 - ii. If month < month of first dose then set day to last day of month
 - iii. If month > month of first dose then set day to first day of month
 - b. If year < year of first dose then set day to last day of month
 - c. If year > year of first dose then set day to first day of month
- 4. If the AE start date is completely missing and the corresponding stop date is completely missing, the AE start date will remain missing.

Missing AE Stop Dates

If the stop date is completely missing and the event is not ongoing (i.e., an outcome is indicated), the stop day will not be estimated.

If only the day of resolution is unknown, the day will be assumed to the last of the month (e.g. ??-JAN-2011 will be treated as 31-JAN-2011)

If the stop date is completely missing and the event is ongoing, the event will be noted as "Ongoing" in the stop date column in the AE listings.

[figure not shown]
Adverse events will be listed for all subjects, including verbatim and coded terms, duration, severity, and relationship to the study drug. TEAE status will be determined based on the imputed dates as defined above.

The incidence and proportion of subjects with TEAEs and SAEs will be summarized by System Organ Class and Preferred Term overall and by the Safety Groups defined in Section 5.1.2.

An overview of TEAEs will be provided that summarizes the incidence of subjects with one or more AE, the incidence of AEs by highest relationship, the incidence of AEs by highest severity, the incidence of AEs by action taken, the incidence of AEs outcome, the incidence of serious adverse events (SAEs), and the incidence of AEs by type of seriousness.

The incidence and proportion of subjects with TEAEs and SAEs will also be summarized overall and by Safery Groups as follows:

- TEAE by System Organ Class, and Preferred Term
- TEAEs by Preferred Term, in descending order of frequency
- TEAEs by highest severity
- TEAEs by highest relationship
- Treatment-related (defined as at least possibly related) TEAEs by System Organ Class, and Preferred Term
- TEAEs resulting in discontinuation from the study
- Treatment-related (defined as at least possibly related) TEAEs by System Organ Class, and Preferred Term, and severity
- TEAEs by dose at time of onset
- TEAEs by time of onset windows, where the denominator for each visit window is the total number of subjects with exposure to drug as of the first day of the window, defined as:

- Treatment Emergent SAE by System Organ Class and Preferred Term
- Treatment Emergent Fatal SAE by System Organ Class and Preferred Term
- Treatment-related SAE by System Organ Class, Preferred Term, and Severity

TEAEs will also be summarized by subgroups as described in Section 6.4.

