# 10.3. Baseline (Visit 2, Day 1/Week 1)

During this visit, the investigator will review all entry criteria, making certain that the potential subject meets all criteria. In addition, the following procedures will be performed:

- AEs will be recorded for all subjects Concomitant medications will be recorded
- Study medication and Subject diary collected and reviewed from previous visit for compliance
- Study medication and diary will be dispensed via IVRS/IWRS
- The next trial visit will be scheduled

Confidential Page 25 of 47

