#### 11.3.1. Adverse Events

An AE is any untoward medical occurrence during treatment with a pharmaceutical product in a subject that does not necessarily have a causal relationship with the treatment being administered. An AE can therefore be any unfavorable and unintended sign (including an

Confidential Page 27 of 47

abnormal laboratory finding), symptom, or disease temporally associated with the use of a medicinal (investigational) product, whether or not related to the medicinal (investigational) product.

An untoward medical event occurring prior to the start of study treatment does not meet the above mentioned definition of an AE. Nevertheless, pre-dosing medical history and physical examination anomalies must be documented in the appropriate section of the eCRF. Each subject will be queried for the occurrence of baseline medical anomalies or conditions prior to study drug administration. Included will be an assessment of their grade (mild, moderate, or severe). These events will be reported under medical history or physical examination. During and following a subject's participation in this trial, the investigator must ensure that adequate medical care is provided to a subject for any AE, including clinically significant laboratory values, related to the trial. The subject will be treated and/or followed up until the symptom(s) returns to normal or stabilizes, as judged by the PI. For data management purposes, for subjects completing the study, follow-up information on AE will be terminated at 30 days from the time of onset of the adverse event.

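### Start-date imputation can override a recorded year or a known stop date, and leaves AEs with neither date undated (minor)

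*SAP*

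**What the plan says.** SAP 6.1.5 and 6.3.1 use the same numbered scheme, in both places subject to medical review.

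- **Rule 1** (no start date). For AEs: "If onset date is completely missing, then onset date is set to date of first dose".
- **Rule 2** (year known, month missing). 2a: in the year of first dose, the start becomes the first-dose date. 2b: in an earlier year, with the stop month and year available, it becomes the first day of the stop month. 2c: in an earlier year otherwise, it becomes 31 December of that year. The AE copy of 2b also refers to the medication stop.
- **Rule 3** (day missing). 3a(i): "If month = month of first dose then set day to day of first dose date". 3a(ii) and 3b: for a month before first dose, the last day of that month.
- **Rule 4** (neither date). "If the AE start date is completely missing and the corresponding stop date is completely missing, the AE start date will remain missing". SAP 6.1.5 says the same of medications.

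These dates then drive classification. For AEs, "TEAE status will be determined based on the imputed dates as defined above"; in SAP 6.1.5 prior and concomitant status also follows the imputed dates. Planned AE summaries include "TEAEs by dose at time of onset" and a table by onset window.

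On AEs before first dose the documents disagree. SAP 6.3.1 captures "Adverse events recorded from the time the Informed Consent Form is signed until 30 days after the end of the trial", and Protocol 10.3 says of Visit 2 that "AEs will be recorded for all subjects". Protocol 11.3.1 says: "An untoward medical event occurring prior to the start of study treatment does not meet the above mentioned definition of an AE". Protocol 11.4.1.2 directs conditions arising after dosing to the AE page.

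**The concern.** An imputation rule should fill in what is unknown without contradicting what is known. Rule 2b discards a recorded year, and five rules do not look at a recorded stop date. AE rule 4 leaves no date where later steps need one.

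At stake are the prior-medication summary and flags, AE durations in the listings, the dose-at-onset and onset-window tables and, for some AEs, whether they count as treatment-emergent. Safety is the study's only objective, so the AE tables are its main output.

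**Working it through.** The SAP's one worked date example, a stop date with the day missing in January 2011, gives 31 January 2011 when the rules are coded as written. The SAP gives no other figure to reproduce. The examples below assume first dose on 15 March 2014.

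**Step 1. Medication rules 2b and 2c.** The start is recorded only as 2010.

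- Drug continuing: 2c gives 31 December 2010.
- Drug stopped 20 June 2014: 2b gives 1 June 2014. From 15 March to 1 June is 78 days, so this is Day 79.
- Difference: 365 + 366 + 365 = 1,096 days to 31 December 2013, plus 152 to 1 June 2014, is 1,248 days.

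The same recorded start thus gives two dates, depending on whether the drug was later stopped, and one of them contradicts the year on file.

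**Step 2. When 2b lands on treatment.** Take all 365 first-dose dates in a year and all stop dates in the first 182 days: 365 × 182 = 66,430 pairs. The imputed start precedes first dose only if the stop falls in the first-dose month and first dose is not on the 1st. A month of n days gives n(n−1)/2 such pairs: 7 × 465 + 4 × 435 + 378 = 5,373. So 66,430 − 5,373 = 61,057 (91.9%) land on treatment. Over 365 days, 133,225 − 5,373 = 127,852 (96.0%). These are shares of date pairs, all with an on-treatment stop. An enumeration that also includes drugs stopped earlier gives a pre-dose start moved onto treatment in 661 of 4,386 (15.1%). It assumes first dose on 15 July 2014, starts on 1,460 consecutive days from 1 January 2012, and durations of 1, 7, 30, 90, 365 and 720 days. None of these figures estimates frequency in the trial.

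**Step 3. Medication rule 2a.** Every year-only start in the first-dose year goes to first dose. The share of that year lying before first dose, all of which is moved, is 14/365 = 3.8% for first dose on 15 January, 181/365 = 49.6% for 1 July and 348/365 = 95.3% for 15 December.

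**Step 4. Known stop dates.** The last column uses the enumeration of Step 2, with every stop date known.

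| Rule | Start on file | Stop on file | Imputed start | Start after stop |
|---|---|---|---|---|
| 1 | none | 5 Mar 2014 | 15 Mar 2014 | 4,343 of 8,760 |
| 2a | 2014 | 5 Mar 2014 | 15 Mar 2014 | 652 of 2,190 |
| 3a(i) | Mar 2014 | 5 Mar 2014 | 15 Mar 2014 | 20 of 186 |
| 3a(ii) | Feb 2014 | 10 Feb 2014 | 28 Feb 2014 | 302 of 1,086 |
| 3b | Mar 2013 | 10 Mar 2013 | 31 Mar 2013 | 1,222 of 4,386 |
| 2b | any earlier year | any | first of stop month | 0 of 4,386 |

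Rules 1, 2a and 3a(i) can put the start at first dose for something already over. Rules 3a(ii) and 3b leave it before first dose, so the date is wrong but the status does not change. Setting the start to the earlier of the imputed start and the known stop reduces every count to 0.

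**Step 5. AE with neither date.** Rule 1 alone gives 15 March 2014. With rule 4 as its exception there is no date. Any ongoing AE of unknown onset is such a case, because it has no stop date. It cannot be assigned a dose at onset or an onset window.

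**The case against.** **Rules 1 and 4.** A reader might infer an outright contradiction. Rule 4 is the more specific and reads naturally as an exception. A reader might also infer that undated AEs drop out of every treatment-emergent table. The documents do not establish that: a figure after the AE stop-date rules is not shown and may hold the definition, and the onset windows are also cut off. Protocol 12.3.3.1 has what looks like the definition with a word missing (new events after administration, or worsening of existing conditions), but it does not mention undated events. What stands is that such AEs cannot enter the two onset tables and that no default is visible.

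**AEs before first dose.** A reader might infer that screening AEs are being turned into treatment-emergent ones. Protocol 11.3.1 and 11.4.1.2 largely exclude such records. A footnote to SAP Table 1, garbled in the text, probably limits AE recording at Visits 1 and 2 to roll-over subjects, who start drug at Visit 1 (SAP 4.2.1). SAP 6.3.1 and Protocol 10.3 point the other way. The effect is therefore conditional, and the texts need reconciling.

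**Medications.** A drug that ended before first dose can still be classed as prior from its stop date; the SAP does not say which date decides. Under 2b a drug taken into treatment is concomitant either way, so only its prior status changes. Wrong TEAE subgroups are a further tempting inference. SAP 6.4 groups by use at Visit 1, and medications are recorded at that visit, so this would follow only if imputed dates were used to decide it. Nor are all year-only starts moved onto treatment: 2c keeps its cases before first dose.

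**Safeguards.** AE dates are required items (Protocol 11.4.1), missing values are queried (SAP 5.3), data receive edit checks and 100% source verification (Protocol 14.4), and imputations have medical review. These make the cases few. They do not correct the rules for the dates that remain missing, and the medical review has no stated criteria.

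**Conclusion.** The point holds, as a minor correction in three parts.

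- **(a)** Medication rule 2b contradicts the recorded year, usually giving an on-treatment start if the drug stopped on treatment. A drug in use before the study then loses its prior status, taking prior to include drugs begun earlier and continued. Rule 2a can also move year-only starts onto treatment, although there the year alone does not settle the order. The AE wording of 2b is a copy error.
- **(b)** Rules 1, 2a, 3a(i), 3a(ii) and 3b can impute a start after a known stop. Under the first three, a medication that ended before dosing can receive an on-treatment start. For AEs this matters only if pre-dose AEs are recorded.
- **(c)** AE rule 4, read as an exception to rule 1, leaves some AEs outside the onset tables and, on the visible text, without a defined treatment-emergent status.

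The number of records with missing dates is not given, so no effect on incidence can be computed. The enumerations rest on assumed, equally weighted dates and show direction only. Nothing here suggests that the study's overall safety conclusions would change.

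**What to change.** 1. **Rule 2b, both sections.** Set the start to the earlier of 31 December of the recorded year and the stop date. In SAP 6.3.1, refer to the AE stop.
2. **All start-date rules, both sections.** If a known stop date is earlier than the imputed start, set the start to the stop date. A drug or AE that ended before first dose is then prior, or not treatment-emergent. Where only the stop month is known and it contains first dose, the month-end stop rule keeps the conservative default.
3. **AE rule 4.** Delete it, so that rule 1 applies, or state that AEs with neither date count as treatment-emergent. Either way, footnote their number in the dose-at-onset and onset-window tables.
4. **Medication rule 4.** It can stay, since a drug with no stop date is taken as continuing. Say that its prior status is unknown, and likewise for a rule 2a drug still in use at first dose, which the cap does not change.
5. **AEs between consent and first dose.** State whether they are recorded, reconciling SAP 6.3.1 and Protocol 10.3 with Protocol 11.3.1, 11.4.1.2 and the SAP Table 1 footnote.

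The cost is a few lines of SAP text and imputation code. The downside is that, if rule 4 is deleted, a few undated AEs are counted at first dose, in the first onset window and at the first dose level; hence the footnote.

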#### Exclusion Criteria:

Subjects will be excluded from the trial if any of the following exclusion criteria apply prior to enrollment:

- 1. History of hypersensitivity to
- 2. History of alcohol abuse or use of recreational drugs within 12 months prior to Visit 1
- 3. History of chronic use of concomitant medications in neurologic or psychiatric illness which would affect the assessment of the safety of the trial medication
- 4. If the investigator feels that participation in this study is not in the best interest of the subject

Investigational product, dosage and mode of administration, and batch number:			

Subjects enrolled following the completion of protocol CLR\_09\_21 will receive as follows:

- Subjects who were randomized to study CLR\_09\_21 (Part 3) will continue to receive the same dose of as they received in study CLR\_09\_21.
- Subjects who were randomized to in the double-blind part of study CLR\_09\_21 (Part 3), will receive the dose of that they received in open-label fixed dose phase (Part 2) of study CLR\_09\_21.

Subjects enrolled in this study who participated in the double-blind phase of study CLR\_09\_21 will temporarily receive blinded study medication in the first 4 weeks dispensed according to the IVRS/IWRS.

**Duration of treatment:** Subjects will continue to receive treatment for the length of the trial.

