6. STATISTICAL ANALYSIS METHODOLOGY

All data collected for this study will be presented in summary tables, listings, and figures (TLFs) as indicated in Appendix 1 of this SAP. Shells for TLFs with enough detail for programming will be provided as a guide to develop the programming SAS codes. These shells will be in sufficient detail to simulate the actual TLFs when they are created from the locked database.

Appropriate descriptive statistics will be computed and displayed (by time point and other key variables as appropriate) for both continuous and categorical variables. For continuous variables, descriptive statistics will include n (the number of subjects with non-missing data), mean, standard deviation (SD), 95% confidence intervals, median, minimum and maximum values. For categorical data, the number and percentage of subjects within each category will be presented. The denominator for percentages will be based on the number of subjects with non-missing data appropriate for summary purposes.

Individual data listings of all data represented on the eCRF and from the clinical laboratory will be presented.

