6.1.6 Exposure and Compliance

6.1.6.1 *Exposure*

Exposure data at each visit starting with Screening will be summarized overall and for each of the safety groups. Specifically, the numbers of subjects for each dose level will be summarized with counts and percentages, and descriptive summaries (mean, median, mode, and standard deviation) of dose at each visit will be provided.

For each subject, total exposure duration will be calculated as the number of days the subject

The exposure duration will be calculated as the date of last dose reported on the final status eCRF— date of first dose + 1. In cases where the date of last dose is not reported or missing, the date of last dose will be considered the date of the last visit with drug return reported. If no visit with drug return reported exists, exposure duration will be set to 1 day.

This exposure data will be summarized overall for the safety population, and by each of the three safety groups described in Section 5.1.2.

Individual subject listings will be prepared.

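### Apart from the onset-window table, TEAEs and SAEs are planned as unadjusted proportions despite open-ended treatment; add exposure-adjusted rates and a time-at-dose denominator

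*SAP*

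**What the plan says.** - **Summary measure.** SAP 6.3.1 plans: "The incidence and proportion of subjects with TEAEs and SAEs will be summarized by System Organ Class and Preferred Term overall", and also by Safety Group. SAP 6.4 adds TEAE incidence by sex, age, race and baseline medication or condition.
- **Denominator.** SAP section 6 sets the general rule: "The denominator for percentages will be based on the number of subjects with non-missing data appropriate for summary purposes". It counts subjects and does not use time.
- **Dose.** One listed table is "TEAEs by dose at time of onset" (Table 14.3.1.11). SAP 6.3.1 states no denominator for it.
- **Onset windows.** Another is the table by onset window (Table 14.3.1.12), in which "the denominator for each visit window is the total number of subjects with exposure to drug as of the first day of the window". The sentence that opens this list applies it both overall and by Safety Group.
- **Length of treatment.** The Protocol Synopsis, under duration of treatment, says: "Subjects will continue to receive treatment for the length of the trial".
- **Exposure.** SAP 6.1.6.1 derives exposure duration for each subject and says: "This exposure data will be summarized overall for the safety population, and by each of the three safety groups described in Section 5.1.2". Neither SAP 6.3.1 nor the table list in SAP Appendix 2 links exposure to adverse events. No rate per person-time, cumulative incidence or time-to-event display is planned for TEAEs.

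**The concern.** Long-term safety is the only objective and efficacy is not evaluated, so the adverse event tables are the main result of the trial. With open-ended treatment, a subject's time at risk depends on enrolment date and on when the subject stops. A crude proportion mixes the event rate with that time. If one Safety Group or subgroup stays on drug longer than another, it will tend to show a higher percentage at the same underlying risk, and a group with early dropout will tend to show a lower one.

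The problem is sharpest by dose. Subjects move between doses: Protocol 12.3.2.2 refers to titration and a maintenance dose, and SAP Appendix 2 lists a dose shift table (Table 14.1.8.1.3). A dose at which more time is spent collects more events at equal risk. Without time at each dose, the table cannot show whether risk differs by dose.

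**Working it through.** The plan has no power, precision or event-rate figure for adverse events, so there is nothing of that kind to reproduce. The check has four steps.

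**1. How unequal could exposure be?** Inputs are the enrolment and exposure targets; retention = completers / enrolled.
- SAP 3.2.1: 250/550 = 45.5% at 26 weeks and 200/550 = 36.4% at 1 year. That leaves 550 − 250 = 300 subjects with under 26 weeks.
- Protocol 12.1: 250/350 = 71.4% and 100/350 = 28.6%. With the 1-year target of 200 from the Protocol Synopsis, 200/350 = 57.1%.

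These counts are minimum or approximate targets, so the percentages are planning values and not forecasts. The documents disagree on them (550 or 350 enrolled; 200 or 100 at 1 year), which needs reconciling separately. At the short end, SAP 6.1.6.1 says: "If no visit with drug return reported exists, exposure duration will be set to 1 day".

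**2. Crude percentage at a constant rate.** Formula: 1 − exp(−rate × years). The rates are assumptions.

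| Rate per year | 4 weeks | 26 weeks | 52 weeks | 104 weeks |
|---|---|---|---|---|
| 0.2 | 1.5% | 9.5% | 18.1% | 33.0% |
| 0.5 | 3.8% | 22.1% | 39.3% | 63.2% |

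A person-time denominator would return 20 or 50 per 100 patient-years in every column.

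Dropout can be added by fitting piecewise-exponential curves to the targets in step 1. Mean exposure in year 1 is then about 0.55 years (550/250/200), 0.66 years (350/250/100) or 0.75 years (350/250/200). At a rate of 0.5, the crude year-1 percentage is 22.6%, 27.1% or 30.0%, against 39.3% if everyone were followed for the year.

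**3. Dose table.** Assume the same rate, 0.5 per year, at both doses, with 2 weeks on a passing dose and 50 weeks on a maintenance dose.
- Passing dose: 1 − exp(−0.5 × 2/52) = 1.9%.
- Maintenance dose: 1 − exp(−0.5 × 50/52) = 38.2%.

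The risk is identical and the figures are far apart.

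**4. Sensitivity: early-onset events.** Assume a hazard of 2.0 per year for 4 weeks, then 0.05.
- Crude: 1 − exp(−(2.0×4 + 0.05×22)/52) = 16.1% at 26 weeks; 1 − exp(−(2.0×4 + 0.05×100)/52) = 22.1% at 104 weeks. Ratio 22.1/16.1 = 1.4.
- Patient-years to first event, per subject: (1 − exp(−2.0×4/52))/2.0 = 0.071 for the first 4 weeks, plus exp(−2.0×4/52) × (1 − exp(−0.05×w/52))/0.05 for the following w weeks. With w = 22 the total is 0.430; with w = 100 it is 1.643.
- Rates: 0.1605/0.430 = 37.3 per 100 patient-years at 26 weeks; 0.2212/1.643 = 13.5 at 104 weeks. Ratio 37.3/13.5 = 2.8, in the opposite direction.

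So the crude percentage is distorted most when the hazard is steady, and the patient-year rate when events cluster early. Neither display is enough alone.

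**The case against.** The strongest reply is that the plan already allows for unequal follow-up. The onset-window table uses the number still exposed at the start of each window, and it is specified by Safety Group as well as overall. It does not need a constant hazard across windows. Exposure duration is also tabulated by Safety Group, and all presentations are descriptive.

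Much of this stands. A reader might infer that TEAEs appear only as crude percentages, or that the onset-window table is a single overall display. SAP 6.3.1 contradicts both. What remains is that this table keeps subjects who leave within a window in its denominator, and does not correct the tables by dose, severity, relatedness, seriousness or subgroup. The window limits are missing from the supplied text, so the within-window effect cannot be sized.

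A reader might also infer that the crude figures mostly reflect time on drug, or that equal risk would look two- to fivefold different between groups. The documents give no event rate, hazard shape or exposure by group or dose. A nearly fivefold ratio (45.1% against 9.5%) needs one group all followed for 3 years, another all followed for 6 months, and a constant rate of 0.2. Step 4 shows a much smaller effect under early onset. An exposure range from days to years is likewise an inference from open-ended dosing and the 1-day fallback.

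Finally, the SAP promises detailed table shells, which were not supplied and may define the dose denominator. The dosing sections are largely blacked out, so actual time at each dose cannot be judged.

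**Conclusion.** The point holds in a limited form. Outside the onset-window table, SAP 6.3.1 relies on proportions of subjects that take no account of exposure, although treatment is open-ended and the SAP's own targets imply wide differences in time on drug. The figures by Safety Group and subgroup can be strongly affected. The dose-at-onset table cannot be interpreted without time at dose, whatever the hazard shape, and SAP 6.3.1 does not state that denominator.

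The size is unknown. From 6 months to 2 years, a constant rate of 0.2 per year moves the crude figure from 9.5% to 33.0%, while the front-loaded example moves it only from 16.1% to 22.1%. Both rest on assumed hazards. The planned tables remain valid as descriptions; the case is for a cheap supplement to them.

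**What to change.** - Keep the crude tables and the onset-window table unchanged.
- Add exposure-adjusted incidence for TEAEs, treatment-related TEAEs and SAEs, overall and by Safety Group: subjects with a first event per 100 patient-years, time running to first event or end of exposure, with exact Poisson 95% confidence intervals.
- In Table 14.3.1.11, state the denominator as patient-years at each dose, and say how a subject who passes through several doses contributes events and time.
- Report how many subjects fall under the 1-day exposure rule, since the new denominator inherits it.
- Footnote the rates: a single patient-year figure assumes a roughly constant hazard and is to be read with Table 14.3.1.12.

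**Cost.** Longer tables and a modest extra derivation of time to first event and time at dose. First and last dose dates, onset dates and dose-change records are already planned. The real downside is interpretive: with early-onset events the patient-year rate can make the longer-exposed group look safer, so it should supplement the existing displays and not replace them.
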